5.1.2. Endpoint 2: Rate of Major Adverse Events (MAEs)

[figure not shown]
The rate of the following MAEs as reported by the Investigators will be assessed during the subject's participation in the study:

- Death within 30 days of index procedure
- Unplanned major (above the ankle) amputation of the target limb
- Clinically-driven TLR and/or TVR of the target limb

The rates of the MAEs will be estimated in the context of a logistic regression, and will attempt to quantify the relationship between covariates or sub-group effects and MAE

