8. STUDY ENDPOINTS

All study endpoints will be assessed by the study treatment group that will include Rutherford classification and type of intervention.

Endpoint 1: Procedural and Lesion Success

Procedural success is defined as a final post-procedural result of < 50% residual stenosis for all treated lesions during the index procedure and without significant angiographic complications, (perforation, dissection type C-F, distal embolization, acute vessel closure) as determined by the Angiographic Core Laboratory.

Lesion success is defined as a final post-procedural result of < 50% residual stenosis for a given lesion treated during the index procedure and without significant angiographic complications, as determined by the Angiographic Core Laboratory.

Endpoint 2: Rate of Major Adverse Events (MAEs)

[figure not shown]
The rate of the following MAEs as reported by the Investigators will be assessed during the subject's participation in the study:

- Death within 30 days of index procedure
- Unplanned major (above the ankle) amputation of the target limb
- Clinically-driven TLR and/or TVR of the target limb

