9. FOLLOW-UP VISITS

All subjects will be followed post-procedure to discharge, at 30 days ±15 days; at 6 and 18 months ±30 days; at 12 and 24 months ±60 days; and annually (±60 days) thereafter until completion of the 5-year post-treatment follow-up or study termination; whichever occurs first. Follow-up visit windows will be calculated from the date of treatment of the index lesion(s) of the target limb.

11.ADVERSE EVENTS

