13.2. BENEFITS

Subject's participation in this study is voluntary. There is no direct additional benefit to subjects enrolled in the study. However, information gathered from this study may help increase the understanding of the clinical and economic outcomes of endovascular treatment of claudication and CLI in patients with lower extremity PAD. These data may lead to expanded national PAD registries and help to standardize PAD definition and treatment guidelines. Ultimately, this knowledge can inform future PAD clinical trials, provide data to help physicians choose the best care for patients, and advance the treatment of lower extremity PAD.

14.PROTOCOL DEVIATIONS

A protocol deviation is defined as an event where the study is not conducted according to the protocol, FDA regulations 21 CFR Parts 50 and 56, and requirements imposed by the reviewing IRB. Protocol deviations that will be collected include, but are not limited to the following:

- Failure to obtain informed consent
- Enrolling a subject who did not meet inclusion criteria, or met exclusion criteria
- Not completing protocol-required examinations or evaluations

15.SITE NON-COMPLIANCE

If excessive protocol deviations are noted, the Sponsor reserves the right to suspend study enrollment until a sufficient system is in place at the site to reduce further deviations, or withdraw the site from participation in the study.

[figure not shown]
16.SUBJECT STUDY EXIT

Subjects will be followed until completion of the study or death, whichever comes first.

Reasons for exiting the study include, but are not limited to, subject lost to follow-up, subject's request to withdraw from the study, or subject death.

17.STUDY MANAGEMENT

This study will be conducted in accordance with the FDA requirements set forth in 21 CFR Parts 50 and 56.

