17.3. EARLY TERMINATION OF STUDY

The Sponsor may terminate this observational study at any time due to the following reasons, but not limited to: low subject recruitment/enrollment, competing studies and financial reasons. Appropriate notification will be provided to all participating Investigators.

18.DATA ANALYSIS

Study data will be analyzed as indicated in the Data Analysis Plan.

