5.1 Procedure and Long-Term Clinical and Economic Outcomes (Study Objective #1)

Procedure and long-term clinical and economic outcomes include lesion success, procedural success, clinical outcomes , major adverse event rates, and economic outcomes. Treatment outcomes at a minimum will be summarized overall and by treatment group. The statistical approach to assess these outcomes is described above.

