5.3.2. Analysis Intervals

†

Endpoint analysis on follow-up data may occur at each specified protocol-defined follow-up window (e.g. 30-day, 6-month, 12-month, and annually thereafter) for which it was collected.

CONFIDENTIAL

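### SAP 5.1.2, as visible, estimates MAE rates over unequal follow-up by logistic regression and does not say how subjects who leave early are counted; late rates and odds ratios depend on that choice

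*SAP*

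**What the plan says.** SAP 5.1.2 lists three MAE components: death within 30 days, unplanned major amputation of the target limb, and clinically driven TLR or TVR. Only death has a time limit. The events "will be assessed during the subject's participation in the study". On method, "The rates of the MAEs will be estimated in the context of a logistic regression", which is also meant to quantify covariate and subgroup effects.

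The length of participation is set elsewhere:

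- Protocol 9 plans follow-up "until completion of the 5-year post-treatment follow-up or study termination; whichever occurs first".
- Protocol 16 gives among the reasons for exit "subject lost to follow-up, subject's request to withdraw from the study, or subject death".
- Protocol 17.3 adds: "The Sponsor may terminate this observational study at any time due to the following reasons".

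Three other passages bear on the analysis:

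- Protocol 8: "All study endpoints will be assessed by the study treatment group that will include Rutherford classification and type of intervention".
- SAP 5.3.2: "Endpoint analysis on follow-up data may occur at each specified protocol-defined follow-up window". This permits fixed windows but gives no denominator.
- SAP 5.1, which covers MAE rates by name: "The statistical approach to assess these outcomes is described above". Only part of that earlier text is public.

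**The concern.** SAP 5.1.1 uses almost the same logistic sentence for procedural and lesion success. It fits there, because the outcome is known when the procedure ends. In 5.1.2 it is applied to an outcome that builds up over as long as 5 years, in subjects observed for different lengths of time.

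A binary logistic model needs a yes or no for each subject and does not use follow-up time. The analyst must therefore decide what to record for a subject lost at, say, 18 months without an MAE. Coding that subject as no MAE pulls the late rate down. Dropping the subject, while keeping those who had an MAE and then left, pushes it up. Two analysts could follow 5.1.2 correctly and report different 5-year rates from the same data.

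MAE is one of the two endpoints in the public text, and the objective covers long-term outcome. Results are to be broken down by Rutherford class and type of intervention. If loss differs between those groups, the odds ratio moves away from 1 even when the true risk is the same.

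**Working it through.** **The plan's own figures.** There are none to reproduce: neither document gives an MAE rate, a loss rate or a late death rate. What follows is an illustration on assumed inputs.

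**Inputs.** The horizons (30 days, 1, 2 and 5 years) come from the visit schedule in Protocol 9. The constant yearly hazards are assumptions: MAE h = 0.15, death as a competing event d = 0.05, independent loss l = 0.05 or 0.10.

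**Formulas.** With s = h + d + l:

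- Share with an MAE seen by time t: E = (h/s)(1 − exp(−st))
- Share lost event-free by time t: L = (l/s)(1 − exp(−st))
- True cumulative incidence: E with l = 0
- Lost counted as no MAE: E
- Lost event-free dropped: E/(1 − L)

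Subjects who die event-free stay in the denominator throughout.

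**At 5 years.**

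- Truth: (0.15/0.20)(1 − exp(−1.00)) = 47.4%.
- l = 0.05: E = (0.15/0.25)(1 − exp(−1.25)) = 42.8%; L = 14.3%; dropped: 0.4281/0.8573 = 49.9%.
- l = 0.10: E = (0.15/0.30)(1 − exp(−1.50)) = 38.8%; L = 25.9%; dropped: 0.3884/0.7410 = 52.4%.

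**By horizon** (ranges run from l = 0.05 to l = 0.10):

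- 30 days: true 1.2%; both shortcuts agree to within 0.1 point.
- 1 year: true 13.6%; 13.3% to 13.0% (counted as no), or 13.9% to 14.2% (dropped). The largest gap is 0.64 point.
- 2 years: true 24.7%; 23.6% to 22.6%, or 25.6% to 26.6%.
- 5 years: true 47.4%; 42.8% to 38.8%, or 49.9% to 52.4%.

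**Group comparison.** Take two groups with identical h and d, one with l = 0.10 and the other with l = 0.05. The odds ratio should be 1.00.

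- 5 years, counted as no: (0.3884/0.6116)/(0.4281/0.5719) = 0.85.
- 5 years, dropped: (0.5242/0.4758)/(0.4994/0.5006) = 1.10.
- 2 years: 0.94 or 1.05. 1 year: 0.97 or 1.03.

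**Sensitivity at 5 years.**

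- Lower MAE hazard, h = 0.05: true 19.7%; 17.6% to 15.8%, or 21.3% to 23.1%; odds ratio 0.88 or 1.11.
- Early events (hazard 0.3083 in year 1 and 0.1028 afterwards, giving the same 47.4%): 44.0% to 41.1%, or 50.7% to 54.0%; odds ratio 0.89 or 1.14.

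**Does death cause the distortion?** No. With l = 0, E equals the true cumulative incidence whatever the value of d, provided event-free deaths stay in the denominator.

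**Does restriction to subjects not lost repair it?** Not fully. Keep only subjects not lost before death or 5 years, whichever comes first. The share kept is K = [d/(d+l)](1 − exp(−5(d+l))) + exp(−5(d+l)). The share kept without an MAE, N, is the same expression with d + l replaced by s. The MAE rate is (K − N)/K.

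- l = 0.05: K = 0.8033, N = 0.4292, rate 46.6%.
- l = 0.10: K = 0.6482, N = 0.3526, rate 45.6%.

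Both are below 47.4%. Subjects who die early have less time in which to be lost, so they are over-represented among those kept, and they also had less time to have an MAE.

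**The case against.** The strongest reply is that the public SAP is incomplete where such a rule would stand. The general analysis text after SAP 3.3 breaks off in mid-sentence, SAP 5.1 points to an approach that is only partly visible, the last sentence of 5.1.2 is cut, and no 5.2 or 5.4 appears. A reader might infer that the plan has no method for incomplete follow-up. The documents do not support that, and the point is limited to the visible text.

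A reader might also infer that the SAP prescribes one ever/never model over all participation. It does not say so. SAP 5.3.2 allows analysis by window, and logistic regression at a fixed time is legitimate when incomplete follow-up is handled properly. But the windows are optional, they sit among general conventions that yield to specific sections, and they do not say how early leavers count. A window alone does not settle the rate.

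It is also fair that the hazards are assumed, that nothing in the documents indicates unequal loss between groups, and that reporting is descriptive (Protocol 5.2) with no success threshold visible. All of this stands. It limits how much is at stake, but leaves unanswered how a subject with incomplete follow-up enters the model.

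Finally, Protocol 16 lists death beside loss and withdrawal, so a reader might count late death as a source of the error. The check above shows that it is not one in itself.

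**Conclusion.** The point holds for the visible text: a method that does not use follow-up time is named for an outcome observed over unequal follow-up, and the handling of early leavers is not stated there. The direction of error depends on the denominator chosen: too low if subjects lost event-free count as no MAE, too high if they are dropped.

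Under the assumed hazards, the 5-year rate is off by 4.6 to 8.6 points downwards (47.4 − 42.8 and 47.4 − 38.8) or 2.5 to 5.0 points upwards (49.9 − 47.4 and 52.4 − 47.4). The 30-day result is practically unaffected and the 1-year result nearly so. With no loss, withdrawal or early termination, the error disappears. The odds-ratio shifts arise only if loss differs between groups.

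What is at stake is the reported late rates and the covariate and subgroup associations, not a formal test of success. This is a cheap improvement, held with medium confidence because non-public text may already deal with it.

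**What to change.** In SAP 5.1.2:

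- Keep logistic regression for 30-day MAE.
- For the later visits in Protocol 9, report the cumulative incidence of MAE from the index procedure, censoring at last contact and treating death after day 30 as a competing event.
- Use a time-to-event model for covariate and subgroup effects, and show numbers at risk by group.
- If logistic regression is kept for later windows, state the window and denominator, and use either a pooled model over follow-up intervals or weighting for loss. Do not rely on restriction to subjects who were not lost.
- If a non-public section already specifies this, cross-refer to it from 5.1.2.

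The cost is SAP wording and a little more analysis work in standard software. No extra patients or visits are required. Event dates and last-contact dates are needed; SAP 5.3 already foresees completing partial dates. The remaining limitation is that censoring, like the interval model or weighting, assumes that loss is unrelated to MAE risk given the covariates, and the SAP should say so.

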6. SAMPLE SIZE AND SUBJECT ENROLLMENT

6.1. SAMPLE SIZE

Approximately 1,200 subjects will be enrolled in this study. The study cohort will be divided into three study arms according to the most severe clinical syndrome present at the time of study enrollment:

- "Claudicant" Arm (Rutherford 2-3) up to 500 subjects
- "CLI Rutherford 4-5" Arm up to 600 subjects
- "CLI Rutherford 6" Arm at least 100 subjects

Based on a unique study design that includes all commercially available endovascular treatment options for lower extremity PAD, the Sponsor will stop the study enrollment once goals for the study are met. However, since the study may be conducted in up to 100 sites in U.S., there may be some subjects enrolled at the same time at multiple sites leading to an overall study cohort exceeding 1,200 subjects.

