6.2. SUBJECT ENROLLMENT

The subject will be considered enrolled in the study when:

- He/she signs an informed consent form (ICF);
- All of the inclusion and none of the exclusion criteria are met; and,
- At least one lesion in the target area of a native vessel is treated with an endovascular device.
 - Note: a) at least one target lesion must be crossed and treated for subject to be considered enrolled in the study.
 - b) if during index procedure, endovascular treatment of the target lesion is converted to bypass, subject is not considered enrolled in the study, therefore no study follow-up is needed.

All efforts will be made to ensure that consecutive subjects are being included in the study. The subject's treatment method(s) will be determined by the treating Investigator. Assignment to study arms will be based upon Rutherford classification at baseline

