3.3 Sample Size

Approximately 1,200 subjects will be enrolled in this study. The study cohort will be divided into three study arms according to the most severe clinical syndrome present at the time of study enrollment:

- "Claudicant" Arm (Rutherford 2-3) 500 subjects
- "CLI Rutherford 4-5" Arm 600 subjects
- "CLI Rutherford 6" Arm 100 subjects

The analysis of data for the LIBERTY study will be based on the objectives outlined in the protocol. Analyses will be conducted on locked clinical study data using SAS software (S Institute, Inc., [name]). In the event an analysis is required is better suited for a statistical package other than SAS, this other package (e.g. R) will be used.
For all analyses, Rutherford category will be defined as each study arm. These will be used as
basis for comparisons of treatment and treatment location as well as clinical and economic outc within the study arm. The primary and secondary specific analyses for descriptive purposes and
planned outcome analyses will be performed as pre-specified in this analysis plan.

Baseline patient characteristics and risk factors will be presented by study arm. This will include frequency distributions for categorical variables and summary statistics for continuous variables as

CONFIDENTIAL	
LIBERTY 360 Data Analysis Plan	Page 6

n	17	11	**	2	n	***	O.	te
7			ш	•	.,		7	
•	r	М	-	~	Μ.			•
	•	•		_	٠.		-	

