5.1.1. Endpoint 1: Procedural and Lesion Success

Procedural success is defined as a final post-procedural result of < 50% residual stenosis for all treated lesions during index procedure and without significant angiographic complications (perforation, dissection type C-F, distal embolization, acute vessel closure) as determined by the Angiographic Core Laboratory.

Lesion success is defined as a final post-procedural result of < 50% residual stenosis for a given lesion treated during index procedure and without significant angiographic complications as determined by the Angiographic Core Laboratory.

The rates of procedural success and of lesion success will be estimated in the context of a logistic regression, and will attempt to quantify the relationship between covariates or sub-group effects and success rates.

[figure not shown]

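### The visible SAP does not say how its logistic models handle site; with ordinary standard errors, intervals for overall rates, and to a lesser degree tests of device type, would be too optimistic if outcomes vary by site

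*SAP*

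**What the plan says.** **Models.** SAP 5.1.1 states: "The rates of procedural success and of lesion success will be estimated in the context of a logistic regression". SAP 5.1.2 states: "The rates of the MAEs will be estimated in the context of a logistic regression", and adds that the model "will attempt to quantify the relationship between covariates or sub-group effects and MAE". Neither section, as far as it can be read, lists covariates or names a variance estimator.

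**Tests and intervals.** SAP 5.3 sets two-tailed tests and confidence intervals at 0.05 and asks for findings to carry a standard deviation, standard error or interval. SAP 5.1 asks for summaries overall and by treatment group.

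**Sites and devices.** Protocol 6.1 states: "Approximately 1,200 subjects will be enrolled in this study", and mentions site numbers in passing: "since the study may be conducted in up to 100 sites in U.S". Protocol 6.2 says that "treatment method(s) will be determined by the treating Investigator". Protocol 8 makes device type an analysis factor: "All study endpoints will be assessed by the study treatment group that will include Rutherford classification and type of intervention".

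**Use of site.** In the visible SAP, site appears once, in 5.3, as a sort key for listings.

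**The concern.** Default logistic regression output takes every observation as independent. In this study there are reasons to doubt that. The same operators select the device and perform the procedure, so both outcome and device type may resemble each other within a site. For MAE there is one more route, because events are counted as the Investigators report them. That route does not apply to procedural and lesion success, which the Angiographic Core Laboratory determines.

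Two things are at stake:

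- **Precision of the rates.** If outcomes vary by site, 1,200 subjects carry less information than 1,200 independent ones, and an ordinary interval for an overall rate is too narrow.
- **Reading of device effects.** If device preference also varies by site, the test of device type rejects too often. In addition, part of the apparent device effect may be a difference between sites.

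Handling only the correlation of several lesions within one subject would not be enough. Procedural success and MAE are counted per subject and would still carry the site correlation.

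**Working it through.** **Inputs from the documents.** N is about 1,200 (Protocol 6.1; the SAP 3.3 arms add up: 500 + 600 + 100 = 1,200). There are up to 100 sites (Protocol 6.1). The mean site size is therefore 1,200/100 = 12, or more if fewer sites take part. Alpha is 0.05, two-sided (SAP 5.3). The plan gives no power, expected rate, interval width or ICC, so it has no figure of its own to reproduce.

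**Assumptions.** Outcome ICC on the observed 0/1 scale: 0.02, 0.05, 0.10. ICC of device type across sites: 0, 0.3 or 1. Coefficient of variation (CV) of site size: 0 or 0.8.

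**Formulas.**
- DE = 1 + (m_eff − 1) × ICC_outcome × ICC_covariate, with m_eff = m(1 + CV²). For an overall rate, set ICC_covariate = 1.
- The standard error should be √DE times larger, and effective N = 1,200/DE.
- Actual alpha of the ordinary test = 2[1 − Φ(1.96/√DE)]; actual coverage = 1 − that value.

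**1. Overall rate, 100 equal sites of 12.** DE = 1 + 11 × ICC.

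| ICC | DE | SE factor | Effective N | Coverage of nominal 95% interval |
|---|---|---|---|---|
| 0.02 | 1.22 | 1.10 | 984 | 92% |
| 0.05 | 1.55 | 1.24 | 774 | 88% |
| 0.10 | 2.10 | 1.45 | 571 | 82% |

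**2. Test of device type, same sites.**

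| ICC | Alpha, device not clustered (0) | Alpha, partly clustered (0.3) | Alpha, fixed within site (1) |
|---|---|---|---|
| 0.02 | 0.050 | 0.058 | 0.076 |
| 0.05 | 0.050 | 0.069 | 0.115 |
| 0.10 | 0.050 | 0.089 | 0.176 |

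The middle column uses DE = 1 + 11 × ICC × 0.3 = 1.07, 1.17, 1.33.

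**3. Sensitivity to site size.** With CV 0.8, m_eff = 12 × 1.64 = 19.68. DE for an overall rate is then 1.37, 1.93, 2.87, and alpha for partly clustered device type is 0.063, 0.083, 0.117. With 50 equal sites of 24, DE for an overall rate is 1 + 23 × ICC = 1.46, 2.15, 3.30.

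**4. Rates within an arm.** Fewer subjects per site count here. At 100 equal sites the means are 500/100 = 5, 600/100 = 6 and 100/100 = 1. For the largest arm, DE = 1 + 5 × ICC = 1.10, 1.25, 1.50. For the Rutherford 6 arm it is 1.00, unless those subjects concentrate at a few sites.

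**5. Simulation of the overall rate.** 4,000 runs, 100 uneven sites with mean 12 and CV 0.8, base logit −1.2. The ICC was set on the latent logit scale at 0.02, 0.05, 0.10, which is about 0.012, 0.030, 0.062 on the observed scale. These are milder scenarios than in steps 1 to 3 and must not be read as the same ones. Ordinary intervals covered 92%, 88%, 82%. Site-robust intervals covered about 94% throughout.

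**6. Simulation of a null covariate.** 1,000 runs per setting, 100 sites of 12, 20% event rate, the same latent ICCs; Monte Carlo error is about 0.7 points. Ordinary tests rejected in 5.0 to 6.2% of runs when the covariate was not clustered, and in 7.0%, 7.7%, 9.8% when it was fixed within site. With site-clustered errors the latter became 5.2%, 5.4%, 4.3%.

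**The case against.** **The SAP never says that subjects are treated as independent.** A reader might infer from the silence that the models ignore site. The documents do not support that. The public SAP text has gaps: SAP 5.1 refers to a statistical approach described above of which only part can be read, and the sentence in 5.1.2 breaks off. No covariates are listed, so site is neither included nor excluded. This objection stands, and the point is limited to what the visible text leaves unspecified.

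**The inflation is not general.** A reader might also infer that all intervals and p-values are too optimistic. That needs a non-zero ICC, which the documents do not give. For tests it also needs a covariate that clusters by site. Protocol 6.2 says only that the Investigator chooses, not how strongly choices differ between sites. This stands for tests: at ICC 0.02 with partly clustered device type, alpha is 0.058. It does not remove the point for overall rates, which carry the full design effect however devices are distributed.

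**The analysis is descriptive.** Protocol 5.2 says so, and the visible text ties no hypothesis or decision rule to these p-values. This lowers the stakes. SAP 5.3 nevertheless plans tests and intervals at 0.05, and a descriptive rate still needs an interval of the right width.

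**Clustered errors do not cure confounding.** Correct. They repair precision only. Separating within-site from between-site device effects takes a further step, and differences between patients within a site remain after it.

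**Conclusion.** The concern holds in a conditional form. The visible SAP names no handling of site for three logistic analyses in a study of up to 100 sites with Investigator-chosen devices. If ordinary standard errors are used and outcomes vary by site, overall rates are reported with too much precision, moderately so at ICC 0.02 and materially at 0.05 or above. The error in device-type tests is smaller and depends on how far device choice clusters by site. Covariates that do not cluster by site are essentially unaffected, and arm-specific rates are affected less than overall ones.

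The sizes rest on assumed ICCs, an assumed covariate ICC of 0.3 for device type and equal sites of 12. Fewer or uneven sites make the effect larger. No confirmatory decision depends on these p-values, so this is an improvement that should be made and not a flaw that invalidates the study.

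**What to change.** In SAP 5.1.1 and 5.1.2, state that the logistic models are fitted by GEE or with cluster-robust standard errors, with site as the cluster and a small-sample correction. Clustering at site level also covers lesions nested in subjects, so one statement serves all three outcomes. If the unpublished part of the SAP already deals with site, a cross-reference is enough.

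For type-of-intervention effects, split device use into its site mean and the within-site deviation, or condition on site, and report the within-site effect. A site random intercept alone blends within-site and between-site information and does not isolate that effect. Say in the report that patient-level confounding remains.

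The cost is a short SAP addition and standard SAS procedures. No new data are needed, since site number is already held for the listings. The downside is somewhat wider intervals.
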